2.3 Eligibility criteria

2.3.1 Inclusion criteria (all of):

- Children aged 2 – 23 months, presenting to a designated health care facility at a participating study site **WITH**
- Diarrhoea per caregiver perception **AND** at least 3 loose or watery stools in the previous 24 hours,
- Diarrhoea for less than 14 days prior to screening **AND** with at least one of the following criteria at presentation:
 - A. Signs of some or severe dehydration as per WHO Pocket Book 2013

- B. Moderately wasted as defined by a mid-upper arm circumference (MUAC) less than 125 mm (but greater than or equal to 115 mm) or a weight-for-length z-score (WLZ) greater than -3SD and less than or equal to -2SD after rehydration during stabilization period or
- C. Severely stunted (length-for-age z-score (LAZ) <-3 SD) **AND**
- Parent or guardian (caregiver) willing to allow household visits on DAY 2 and DAY 3 and willing to return to facility on DAY 90 **AND**
- Parent or guardian (caregiver) provides a consent for trial participation on behalf of the child, based on local standards

Exclusion criteria (any one of):

- Dysentery (gross blood in stool reported by caregiver or observed by healthcare worker [HCW]),
- Suspected *Vibrio cholerae* infection (determined according to WHO guidelines or clinical suspicion),
- Previously or currently enrolled in the ABCD study,
- Concurrently enrolled in another interventional clinical trial,
- Sibling or other child in the household enrolled in the ABCD study and currently taking study medication,
- Signs of associated infections (pneumonia, severe febrile illness, meningitis, mastoiditis or acute ear infection) requiring antibiotic treatment,
- Documented antibiotic use in the 14 days prior to screening (not including standard use of prophylactic antibiotics, i.e. co-trimoxazole use in HIV-exposed children),
- Documented use of metronidazole within the last 14-days,
- Known allergy or contraindication to azithromycin antibiotics,
- Severe acute malnutrition (SAM) defined as WLZ less than -3 SD, or MUAC less than 115 mm, or edema of both feet, OR
- Living too far from the enrolment health center to ensure adequate Directly Observed Therapy (DOT) on DAY 2 and DAY3

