Current efforts to reduce antimicrobial use are failing and new strategies and approaches to change prescribing practices and patient demand factors are urgently required. Given the widespread and inappropriate use of antibiotics, efforts to identify and focus use in a sub-population of children with well-defined and highly specific acute diarrhoea episodes could reduce overall use. This dynamic has been observed for other infectious diseases³⁴. The ABCD Trial results, if robust, might thus, paradoxically, lead to reduced use of antibiotics and lessen the ecologic pressure pushing resistance. To further limit antibiotic use, the ABCD trial enrolment criteria have been made as strict as possible, only including children whom a guardian brings to a health facility and who has at least moderate dehydration, moderate wasting or severe stunting.

The mortality estimates used to determine the sample size required to achieve adequate power and based on a large multi-center observational study (GEMS), a related observational study (GEMS1a) and meta-analyses of earlier cohort studies in Sub-Saharan Africa and Southern Asia. Although the estimates used are considered conservative based on other available data and preference was given to the selection of sites thought to experience high diarrhoea associated mortality, it is conceivable that there will be fewer mortality events observed in this trial, which would have implications for study power.

² Eberly MD, Eide MB, Thompson JL, Nylund CM Azithromycin in Early Infancy and Pyloric Stenosis. American Academy of Pediatrics. Published Online (date) February 16, 2015, doi: 10.1542/peds.2014-2026

³ Qazi, S.A, Rehman, G.H, Khan, M.A. Standard management of acute respiratory infections in a children's hospital in Pakistan: impact on antibiotic use and case fatality. Bull. WHO, 1996, 74 (5): 501-507

⁴ Gouws, E. Bryce, J., Habicht, J.P., et. al. Improving antimicrobial use among health workers in first-level facilities: results from the Multi-Country Evaluation of the Integrated Management of Childhood Illness strategy. Bull. WHO, 2004 82 (7): 509-515

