Recruitment will begin at the Dhaka and Mirpur hospitals after IRB approval (both WHO and icddr,b). A subject enrolment and follow up team (includes physicians, nurses, research assistants, health workers, and health attendants) responsible for enrolled patients at day 1 and during subsequent hospitalization (if required) and another mobile team (includes research assistants, health workers) focused solely on community sensitization, directly observed therapy, and follow-up into the community will be placed at each of the two hospitals. Study staff will work closely with hospital staff to determine when there is a potentially eligible child either in the oral rehydration therapy (ORT) corner or in the short stay ward (SSW). The children with some or severe dehydration will be treated in the SSW until dehydration is fully corrected. Stabilization/rehydration period will not exceed 6 hours before enrolment. The ORT corner manages diarrhoeal children without dehydration and those do not require any antibiotics and are observed for 2 hours. Children with no dehydration but having moderate malnutrition using MUAC (>115 to <125 mm) or having moderate stunting (<-2SD for length for age of the WHO median) or moderate wasting (<= 2SD for weight for length of the WHO median) will be enrolled from ORT. Children with MSD will be enrolled from the SSW. The study co-coordinator (senior medical officer) and study physician will also participate in the daily morning health discussion to sensitize caregivers about the study and actively identify potentially eligible participants. The follow-up team will be deployed into the community as per the protocol and they will decide whether a child needs to seek care at a facility as per standard WHO guideline.

Screening/Enrolment

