After an eligible child has been identified with the screening described above, the study research assistant will approach the primary caregiver of the child and describe the study procedures. The research assistant will explain that the child and caregiver must be willing to be visited at their home for directly observed therapy (DOT) for the next two days, be willing to be visited at their home for follow-up 90-days after enrolment, and be willing to provide a stool sample from the child at enrolment and at the 90 and 180 day follow ups (for a subset of children). If the caregiver is interested in participating, the study staff will obtain informed consent. Informed consent will be conducted in local language (Bangla). The parent or guardian (primary caregiver) must sign written informed consent (or provide a witnessed thumbprint if not literate) prior to enrolment.

The study physician will interview the primary caregiver of the child to collect required information in the case report form. A stool sample will be collected and processed according to study protocol. The follow-up research assistant will collect detailed contact information from the caregivers using a standardized patient locator form, including drawing of a map of home location with the help of the caregiver. We will also ascertain mobile phone information of the caregiver for adherence assessment, follow-up visit reminders, and home tracing. If a caregiver does not have a personal mobile phone we will obtain the mobile phone information of a household member or friend of the caregivers' choosing. We expect less than 5% of participants to be without cell phone access based on our recently accomplished post discharge follow-up study in severely malnourished pneumonia children [6].

Following consent, each participant will be assigned a unique study Patient Identification Number (PID). A card detailing the PID and the medical personnel responsible for enrolment will be given to the primary caregiver of enrolled children. The patient locator form will be the only link between the PID and the participant's name and will be stored in a locked file cabinet at each site accessible by only the study physician/nurses and follow-up staff for the purpose of patient tracing. Patient enrolment in Dhaka hospital will be done 24 hours a day, 7 days a week and in Mirpur hospital from 9 am to 5 pm in each day.

Standard of Care

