4.2 Per protocol (PP) analysis and definition of protocol deviation

The following participants will be excluded from the per protocol analysis:

- (i) participants with a primary outcome missing for each respective outcome
- (ii) Participants who have been non-adherent to treatment. Adherent participants are defined as those receiving all 3 doses of the study regimen in the first three days of trial participation. The exception to this is if a participant died during this 3-day period. Such participants will be included in the PP analysis.
- (iii) Participants whose follow-up visit for anthropometry was outside the window allowed by protocol will be excluded from per protocol analysis of Primary Outcome 2 (change in length-for-age z-score) and Secondary Outcome 1 (acute wasting), but will be included in Primary Outcome 1 (mortality).
- (iv) Participants who were ineligible or should not have otherwise been enrolled into the study

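### The Bangladesh recruitment plan conflicts with core eligibility on stunting, and no text says which rule prevails

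*Protocol*

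**What the plan says.** Protocol 2.3.1 requires at least one of three risk criteria: (A) some or severe dehydration; (B) moderate wasting, by MUAC or weight-for-length z-score (WLZ); or (C) "Severely stunted (length-for-age z-score (LAZ) <-3 SD". Section 3.2 repeats severe stunting as the stunting criterion. So does section 11, which presents strict enrolment criteria as a limit on antibiotic use and lists "at least moderate dehydration, moderate wasting or severe stunting".

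The Recruitment text of section 13.1 (Bangladesh) deals with non-dehydrated children seen in the oral rehydration (ORT) corner. After a MUAC criterion it continues "or having moderate stunting", which it sets at LAZ below -2 SD, adds moderate wasting as a further alternative, and says that these children "will be enrolled from ORT". The Screening/Enrolment text that follows begins "After an eligible child has been identified with the screening described above" and goes on to consent. The Intervention text then covers study drug.

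Two general sections bear on precedence. Section 4 leaves site-specific recruitment plans to the site documents. Section 4.1 says that screening uses the core inclusion and exclusion criteria on a standardised form.

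In the SAP, section 4.1 keeps every randomised child in the ITT analysis. Section 4.2(iv) removes from the per-protocol analysis "Participants who were ineligible or should not have otherwise been enrolled into the study". Sections 4.5 and 10.3 classify reason for enrolment as dehydration, moderate wasting or severe stunting.

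**The concern.** The 13.1 sentence is current protocol text and says who is to be enrolled. Its stunting threshold is one z-score unit looser than 2.3.1. The other six site plans refer eligibility back to the study protocol, procedures or criteria; Bangladesh alone writes out anthropometric cut-offs.

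If staff followed 13.1, some randomised children would lie outside the population that 2.3.1 and section 11 describe. Those allocated to azithromycin would receive it despite the section 11 limit. All of them would stay in ITT and leave the per-protocol set, at one site. A child enrolled on moderate stunting alone would also fit none of the three SAP reasons for enrolment. While the protocol gives two rules, the SAP cannot say unambiguously who was ineligible.

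**Working it through.** **1. The two rules side by side, for a child without dehydration**

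| Criterion | Protocol 2.3.1 | Protocol 13.1 |
|---|---|---|
| Stunting | LAZ below -3 SD | LAZ below -2 SD |
| MUAC | at least 115 and below 125 mm | above 115 and below 125 mm |
| WLZ | above -3 SD, up to and including -2 SD | upper limit only (printed without a minus sign, possibly a text-extraction loss) |

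Take a child with no dehydration, MUAC of 125 mm or more, WLZ above -2 and LAZ between -3 and -2. Criteria A, B and C all fail, so the child is ineligible under 2.3.1. Under 13.1 the stunting criterion alone suffices, so the child is enrolled. Children with LAZ below -3, or with qualifying wasting, are eligible under both rules. The conflict is confined to this band.

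**2. Which rule governs.** Section 4.1 points to the core criteria. Section 13.1 points to its own preceding text. Section 4 delegates recruitment plans to the sites and does not mention eligibility. There is no precedence clause.

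**3. The planned sample size, reproduced.** Inputs from Protocol 10.3: control mortality p1 = 0.027, relative risk 0.65, 90% power, 10% loss, 1:1 allocation. Two-sided alpha is 0.05.

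- p2 = 0.65 × 0.027 = 0.01755; mean p = 0.022275.
- n = [1.960 × √(2 × 0.022275 × 0.977725) + 1.282 × √(0.027 × 0.973 + 0.01755 × 0.98245)]² / (0.027 - 0.01755)² = 5,123 per group.
- 5,123 / 0.90 = 5,693, against 5,696 stated.
- 5,696 × 1.009 = 5,747, consistent with the stated 5,750.

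With 5,750 × 0.90 = 5,175 evaluable per group, power is 90.3%.

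**4. Possible dilution (illustration).** The documents give neither the number nor the mortality of children in the band. Assumptions: Bangladesh enrols N children, from 11,500 / 7 = 1,643 up to the 2,000 cap; a share f of them is in the band; their control mortality is m; the relative risk stays at 0.65. Then w = N × f / 11,500, and pooled control mortality is pc = (1 - w) × 0.027 + w × m. Power is recomputed at pc and 0.65 × pc with 5,175 per group.

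| N | f | Children | w | m | pc | Power |
|---|---|---|---|---|---|---|
| 1,643 | 10% | 164 | 1.4% | 2.0% | 2.69% | 90.2% |
| 2,000 | 10% | 200 | 1.7% | 2.0% | 2.69% | 90.2% |
| 2,000 | 10% | 200 | 1.7% | 0.5% | 2.66% | 89.9% |
| 2,000 | 20% | 400 | 3.5% | 2.0% | 2.68% | 90.0% |
| 2,000 | 20% | 400 | 3.5% | 0.5% | 2.62% | 89.4% |
| 2,000 | 50% | 1,000 | 8.7% | 0.5% | 2.51% | 88.1% |

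At 10-20% of a full site the loss is under one percentage point. At the extreme of 50% and 0.5% it is about two. Under 1:1 allocation, 200-400 such children would mean about 100-200 given azithromycin.

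These figures use the planned total. The SAP Introduction says that recruitment was halted early, so they measure dilution against the plan and not the power achieved.

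**The case against.** The strongest reply is that the core text already controls screening. Section 4.1 requires the core criteria on a standardised form. Sections 8 and 12 add training to standardise screening and enrolment, monitoring of adherence to enrolment criteria, and supervisor checks on use of the standardised criteria. The SAP's three reasons for enrolment suggest, without proving it, that data capture followed 2.3.1. The 13.1 sentence also looks like leftover wording: the version history records the removal of moderate stunting at version 6.0, and 13.1 still discusses ciprofloxacin sensitivity although that drug was dropped at the same version.

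Most of this stands. These controls may well have stopped such enrolments. But they do not remove the contradiction, because 2.3.1 and 13.1 are both current text and 13.1 does not refer its screening back to 2.3. The version history only corroborates the likely origin; the point does not depend on it.

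It is also fair that the SAP already plans much of the handling. Ineligible children leave the per-protocol set, protocol deviations are tabulated by arm and by country, and moderate and severe stunting appear in the baseline tables. But a prevalence of moderate stunting does not show who lacked every other criterion, and the deviation count depends on which eligibility rule was applied. Lastly, recruitment stopped in July 2019, so editing 13.1 now changes no child's enrolment. That is correct, and it makes the check of enrolled children the part of the remedy that matters.

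**Conclusion.** The inconsistency is real. A non-dehydrated, non-wasted child with LAZ between -3 and -2 could be randomised under 13.1 although ineligible under 2.3.1, and nothing in the documents settles precedence.

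A reader might infer that Bangladesh did randomise ineligible, lower-risk children and so weakened the mortality comparison. The documents do not support that:

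- They contain no enrolment data on this band, and section 4.1 directs staff to the core criteria.
- Lower risk rests only on the Background statement that risk of death was associated with degree of stunting. No mortality figure is given for the band.
- The 10-20% share is an assumption with no source, and even so the loss of planned power is below one point.

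Nor does the conflict threaten the validity of the randomised comparison. Ineligibility here depends on baseline measurements alone, so it should affect both arms alike.

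What remains is possible azithromycin exposure outside the stated population, for about half of any such children, and uncertain classification for the per-protocol and reason-for-enrolment analyses. The number of children is unknown but can be found from recorded data. No view is taken here on which stunting threshold is clinically right.

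**What to change.** 1. Reconcile the Bangladesh recruitment sentence in 13.1 with 2.3.1 on stunting and on the MUAC and WLZ limits, and state that the eligibility section governs the site plans if that is the intention.
2. From recorded baseline LAZ, WLZ, MUAC and dehydration status, list the Bangladesh children who met none of criteria A to C in 2.3.1. Use the 2.3.1 cut-offs: SAP Table 1 counts LAZ of exactly -3.0 as severe stunting, whereas 2.3.1 requires a value below -3. Build the list from baseline data alone, before treatment allocation is attached.
3. Keep the listed children in ITT, apply SAP 4.2(iv) to them in the per-protocol analysis, and report their number by arm among the protocol deviations. In the analyses under SAP 4.5 and 10.3, state that they fall in none of the three enrolment-reason categories.

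The cost is one edited sentence, one query on data that the SAP already tabulates, and one line in the deviation table. The planned sample size does not change. If the list is empty, one sentence saying so closes the point.

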13.2 India

Description of the Study Site

The study will be undertaken in Meerut district of Western Uttar Pradesh, India covering a population of 3,720,000 (~14.6% constitutes the under-five population). District is divided into 3 Tehsils: Mawana, Meerut and Sardhana and 12 blocks: Kharkhoda, Daurala, Hastinapur, Jani, Machhara, Mawana Kala, Meerut, Pariskhitgarh, Rajpura, Rohata, Sarurpur and Sardhana. Both public (Department of Health and Family Welfare) and private sector agencies (hospitals, nursing homes and clinics) provide health services in Meerut district. The site carries a high disease burden in terms of water borne diseases like diarrhoea, dysentery and typhoid, acute respiratory illness especially in young children. As per the Annual Health survey of Meerut (2011-2012), the incidence of diarrhoea is about 11.7% in children 0-6 yrs (Rural 12.8% and urban 9.9%) (upnrhm.gov.in/site-files/IMR_AHS.pdf; Data from the CMO Office, Meerut). Overall mortality associated with diarrhoeal diseases is estimated to be 0.13%. The urban poor constitute a high-risk group with regard to child health and have a substantially higher prevalence of child morbidity and mortality due to malnutrition and infectious diseases. A study conducted in the slums of Meerut reported the prevalence of diarrhoea to be as high as 24.2% among the under five children (UHRC, 2007-08).

Study Recruitment Facilities and Catchment Area

The proposed study will be carried out in two tertiary care hospitals [1 private- Subharti Medical College (SMC) and 1 government- Lala Lajpat Rai Memorial (LLRM) Medical College], 1 district hospital and 9 of the 12 CHCs in rural areas and their catchment area. Diarrhoea caseload in these facilities is high as most of the children (meeting criteria for “moderate to severe diarrhoea”) get referred to these facilities. As part of the National Rural Health Mission (NRHM) ASHA workers have been providing community health services. They will be used for referring diarrhoeal cases to the facilities.

Catchment Area: In rural setting we have identified the villages covering ~1 lakh population to define the catchment area under each CHC. In urban setting, the city area around the health facilities (~7-10 Kms radius) has been identified as catchment area.

Community mobilization: Before the start of the study discussions will be held with the Director, NRHM and CMO, Meerut district. PI and Co-PI will visit all the selected health facilities and explain the study purpose to the health personnel. Village level meetings will be held to mobilize the community support and generate awareness.

Study Team: The study team will have four different levels of study personnel with specific roles and responsibilities. The study team will include Project manager, one study coordinator, one-supervisor/quality control personnel at SMC, one at LLRM, 1 at District Hospital and one at each of the CHCs. They will work closely with the hospital staff to identify and recruit children. Additionally mobile study team – 2 members at SMC, 2 at LLRM, 2 at district hospital, 3 at CHCs (covering 3 CHCs per person) will be deployed. These members will be provided motorbikes and they will be responsible for direct observational therapy and follow up visits. In addition there will be Lab manager, data manager, lab staff, and anthropometry and quality control team members.

Screening and Enrolment

A surveillance system will be set up at SMC, LLRM and District hospital OPD/Emergency wards will identify all diarrhoea cases and screen them for eligibility according to study procedures. For those children meeting the eligibility criteria, enrolment supervisor will approach the parents/caregiver and explain the study procedures to them. H/She will explain that the child and caregiver must be willing to be visited at home (or at a pre-determined nearby facility) for directly observed therapy (DOT) for the next two days, be willing to return to the health facility for the follow-up visit on day-90 after enrolment, and be willing to provide a stool sample from the child at enrolment and possibly at 90 days (for a subset of randomly selected children). If the caregiver is interested in study participation, informed written consent will be obtained in local language (Hindi).

After obtaining consent, the enrolment supervisor will complete the Enrolment form and record the baseline information such as socio-demographic characteristics, breastfeeding and vaccination history. A stool sample will be collected in a sterile stool container and processed according to study protocol

Following consent, each participant will be assigned a unique subject identification number. A card will be given to the caregiver of enrolled children providing contact information in case of an emergency. Subject identification information will be stored in a locked file cabinet accessible by only the project manager and study coordinator for the purpose of patient tracing.

At the time of discharge contact details including phone number of the caregiver or relative/friend (in case personal number not available) will be obtained to send follow-up visit reminders and for follow up visits We will also take the help of ASHAs (part of government health system) working in the community to locate the houses.

Standard of Care

All enrolled children will receive standard of care for diarrhoea management per WHO and National Health guidelines.

In children with acute diarrhoea, this will include:

- a. Standardized assessment of hydration status
- b. Rehydration and maintenance fluids with intravenous or oral rehydration solutions (ORS) as indicated
- c. Oral zinc therapy for 10-14 days (10 mg for infants < 6 months old; 20 mg for 6 months and older)
- d. Recommendation for increased fluid intake and continued feeding at home
- e. Instructions on when to seek follow-up care.

Delivery of Intervention

Following enrolment, stool sample collection, and acute management, the study supervisor will identify the pre-labeled intervention bottle corresponding to the Subject ID. The supervisor will explain the treatment regime and visitation schedule of the mobile team for monitoring the intervention dose in the subsequent 2 days and will counsel the caregiver on the importance of adhering to the intervention. Study supervisor will monitor the first dose administered to the child at the health facility. Enrolled subjects information will be entered into the database in real time and follow-up visit schedules will be prepared every evening for visits falling on the next day. The program manager along with study supervisor will allocate visits to mobile team workers of a particular area. In case the child is still in hospital information will be sent to the hospital supervisor. All children enrolled will be visited on Day-2 and 3 by the mobile team to observe the dose of intervention given. Outcome information will be recorded in a predesigned questionnaire in the netbook. Subjects needing medical attention will be advised to visit health facilities. For children still in hospital, hospital supervisor will give the dose.

Follow-up Visits

A follow-up contact will be established between day 40 and 50 to ascertain vital status (usually a phone call). If in case the contact couldn't be established with the family after four attempts the study worker will be advised to visit the household. A standardized questionnaire will be used to record the vital status of the child and to remind the caregiver of the day-90 follow-up visit at the facility.

All enrolled children and caregivers will be scheduled to visit the health facility on day-90 (between day-80 and -100) following enrolment to ascertain vital status and record anthropometric measurements. Prior to the scheduled visit i.e. 2 days in advance text message reminders will be sent to the mobile phone number provided. During this visit, the study supervisors stationed at the facility will take anthropometric measurements and mortality information since the last time the child was seen by study staff. If the participant does not return at their scheduled time, study supervisor will attempt to make contact with the caregiver via mobile phone; if the contact could not be established study team member will visit the participant household and facilitate them to visit the nearest health facility.

If at any of the follow-up visits, a caregiver reports that a child has died an appointment for verbal autopsy will be set up at home to ascertain the cause of death. The study staff trained in verbal autopsy will review the hospital records (if available) and conduct interviews in the local language 'Hindi' describing the events that preceded the death.

Quality Control: For overall supervision, two mobile supervisory staff will be recruited to perform quality checks. 10% among the enrolled households will be selected randomly from the visit schedule using a computer algorithm. Quality control team will visit these households to check if the required visitation by the mobile community team were conducted as per protocol. In 5% households they will collect repeat data, which will be used by the program manager to verify the accuracy of data. Random quality controls check of anthropometry data and repeat measurement will be done in visits requiring anthropometric measurements.

Data Management: All data will be electronically captured in real time using laptops in the facilities and tablets or netbooks in the community. At the end of each day, all data from various facilities and community will be synchronized with the central server. The database will be password-protected and all site staff responsible for entering data will have unique usernames and passwords controlled by the data manager. The data manager will generate the follow-up visit schedules on daily basis for each facility. Additionally, the data manager will evaluate data daily and generate reports on a weekly basis to identify any missing information or erroneous data. An audit trail will be maintained for recording any changes to the existing data.

Ethical Review:

The study protocol and associated research instruments will be submitted to the Subharti Medical College Ethical Review Board and Lala Lajpat Rai Memorial College Ethical Review Board for approval.

